### **9.3 Analysis of Laboratory Data**

Data collected from central and local laboratories, including additional laboratory testing due to an SAE, will be used in all analyses, except for Baseline, where SAE-related laboratory assessments on or before the first dose of study drug will be excluded.

Baseline is defined as the last available measurement before Study M16-063 study drug administration. The clinical laboratory tests defined in the protocol operations manual (e.g., hematology and clinical chemistry) will be summarized.

Mean change from baseline to each applicable post-baseline visit will be summarized for selected laboratory variables, with the number of observations, baseline mean, and visit mean, at each visit in Study M16-063 and Study M16-763 for each treatment group. An ANOVA model with only treatment as a factor, not controlling for baseline, will be used to test statistical significance for the mean change from baseline among different arms.

The baseline and post-baseline laboratory observations will be categorized as Grade 1, Grade 2, Grade 3, and Grade 4 according to OMERACT criteria (Rheumatology Common Toxicity Criteria v.2.0). For creatine phosphokinase and creatinine, NCI CTC criteria will be used.

For each laboratory variable, shift tables will be generated that cross tabulate the subjects as deemed appropriate by "as treated" treatment group:

- Category of the baseline value versus category of the final value.
- Category of the baseline value versus maximum category.
- Category of the baseline value versus minimum category.

Note that the minimum/maximum category is used, rather than the category of the minimum/maximum value. The two may be different due to variation in the reference range.

No statistical tests will be performed for this analysis.

Laboratory abnormalities will be evaluated based on Potentially Clinically Significant (PCS) criteria ([Appendix C](#)). For each laboratory PCS criterion, the number and percentage of subjects who have a laboratory value meeting the criteria will be summarized. Listings will be provided to summarize subject-level laboratory data for subjects meeting PCS criteria.

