According to FDA's Guidance for Industry "Drug-Induced Liver Injury: Premarketing clinical evaluation" (July 2009), when aminotransferase (AT) abnormalities indicating hepatocellular injury are accompanied by evidence of impaired hepatic function (bilirubin elevation  $> 2 \times \text{ULN}$ ), in the absence of evidence of biliary obstruction (i.e., significant elevation of ALP) or some other explanation of the injury (e.g., viral hepatitis, alcohol hepatitis), the combined finding (i.e., Hy's Law cases) represents a signal of a potential for the drug to cause severe DILI.

For the purpose of assessing for potential Hy's law cases, the frequencies and percentages of subjects with post baseline liver-specific function test values that meet the following criteria of potential clinical interest will be summarized by "as treated" treatment group:

- $\text{ALT} \geq 3 \times \text{ULN}$
- $\text{ALT} \geq 5 \times \text{ULN}$
- $\text{ALT} \geq 10 \times \text{ULN}$
- $\text{ALT} \geq 20 \times \text{ULN}$
- $\text{AST} \geq 3 \times \text{ULN}$
- $\text{AST} \geq 5 \times \text{ULN}$
- $\text{AST} \geq 10 \times \text{ULN}$
- $\text{AST} \geq 20 \times \text{ULN}$

- Total Bilirubin Level (TBL)  $\geq 2 \times$  ULN
- Alkaline phosphatase  $\geq 1.5 \times$  ULN
- ALT and/or AST  $\geq 3 \times$  ULN and concurrent TBL  $\geq 1.5 \times$  ULN
- ALT and/or AST  $\geq 3 \times$  ULN and concurrent TBL  $\geq 2 \times$  ULN

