## **11.0 Interim Analysis**

An interim analysis to review long-term safety and efficacy will be conducted after Study M16-063 Week 12 database lock and analysis. The descriptive statistics will be presented for key efficacy and safety endpoints with all available data at the interim analysis. Key efficacy endpoints include DAS28(CRP), CDAI, ACR20/50/70, Patient's Assessment of Pain [using visual analog scale, VAS], and HAQ-DI. Key safety endpoints include overview of TEAE, TEAEs reasonably possibly related to study drug, SAEs, TEAE leading to death, AESIs, mean change from baseline for hematology and chemistry, PCS for hematology and chemistry and liver-related elevations.

Unblinded interim analyses for safety will be conducted by a DMC to review safety. The sponsor, study sites and subjects will remain blinded for the duration of the study until the database lock of Study M16-063.

An internal data monitoring committee (DMC) will review unblinded safety data from the ongoing study. The primary responsibility of the DMC will be to protect the safety of the subjects participating in this study. A separate DMC charter has been prepared outside of the protocol and describes the roles and responsibilities of the DMC members, frequency of data reviews, relevant safety data to be assessed, and expectations for blinded communications.

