## **Appendix C. Potentially Clinically Significant Criteria for Safety Endpoints**

The criteria for Potentially Clinically Important (PCS) laboratory findings are determined by OMERACT criteria in Table C-1, and the PCS criteria for vital sign findings are described in Table C-2.

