**Rheumatology Common Toxicity Criteria v.2.0**

**Based on Woodworth TG, et al. Standardizing assessment of adverse effects in rheumatology clinical trials II. Status of OMERACT Drug Safety Working Group May 2006: OMERACT 8. Standardizing Assessment and Reporting of Adverse Effects in Rheumatology Clinical Trials: Enabling Description of Comparative Safety Profiles for Antirheumatic Therapies**

K3. Neutropenia (× 1000)	1.5 – 1.9	1.0 – 1.4	0.5 – 0.9	< 0.5
K4. Lymphopenia (× 1000)	1.5 – 1.9	1.0 – 1.4	0.5 – 0.9	< 0.5
K5. Platelets (× 1000)	75 – LLN	50 – 74.9	20 – 49.9; platelet transfusion required	< 20; recurrent platelet transfusions
L. Chemistry				
L1. Hypercalcaemia (mg/dl)	1.1 × ULN – 11.5	11.6 – 12.5	12.6 – 13.5; or symptoms present	> 13.5; or associated coma
L2. Hyperglycemia (mg/dl) Fasting	140 – 160	161 – 250	251 – 500	> 500, or associated with ketoacidosis
L3. Hyperkalaemia (mmol/l)***	5.5 – 5.9	6.0 – 6.4	6.5 – 7.0 or any ECG change	> 7.0 or any arrhythmia
L5. Hypocalcaemia (mg/dl)	0.9 × LLN – 7.8	7.7 – 7.0	6.9 – 6.5; or associated with symptoms	< 6.5 or occurrence of tetany
L6. Hypoglycemia (mg/dl)	55 – 64 (no symptoms)	40 – 54 (or symptoms present)	30 – 39 (symptoms impair function)	< 30 or coma
L7. Hyponatraemia (mmol/l)***	-	125 – 129	120 – 124	< 120
L8. Hypokalaemia (mg/dl)***	-	3.0 – 3.4	2.5 – 2.9	< 2.5

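### The laboratory PCS rule in SAP 9.3 sets no post-baseline window and no worse-than-baseline condition, so unchanged entry abnormalities can be counted for criteria defined by absolute levels or ULN multiples

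*SAP*

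**What the plan says.** The counting rule in SAP 9.3 is: "For each laboratory PCS criterion, the number and percentage of subjects who have a laboratory value meeting the criteria will be summarized". Listings of subject-level data follow for the same subjects, with no columns specified. Appendix C says that PCS "laboratory findings are determined by OMERACT criteria in Table C-1", a table of Grades 1 to 4, and names no grade as the PCS cut-off.

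Four other statements bear on how the rule is read:

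- SAP 9.3 opens: "Data collected from central and local laboratories, including additional laboratory testing due to an SAE, will be used in all analyses". The one exclusion it adds concerns SAE-related tests when the baseline value is chosen.
- "Baseline is defined as the last available measurement before Study M16-063 study drug administration". This is the feeder-study baseline for every group, including subjects who took placebo there and ABBV-599 here.
- The liver table later in SAP 9.3 is restricted in terms to "the frequencies and percentages of subjects with post baseline liver-specific function test values".
- SAP 9.3 also plans shift tables of baseline grade against final, maximum and minimum grade.

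SAP 11 lists among the key interim safety endpoints "PCS for hematology and chemistry and liver-related elevations". It also lists mean change from baseline for hematology and chemistry. It does not list the shift tables.

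**The concern.** A PCS table by treatment group is normally read as showing how often the drug pushes a laboratory value across a threshold. The rule as written does not isolate that. Most haematology and many chemistry rows of Table C-1 are absolute levels or ULN multiples. The row "K4. Lymphopenia" is the clearest case: Grade 1 is 1.5 to 1.9 (× 1000) with no reference to baseline, so a subject who enters at 1.7 and stays at 1.7 meets it. Lymphopenia is also a potential ABBV-105 risk in protocol 2.2 and an adverse event of special interest in protocol 6.1.

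Entry abnormalities are plausible, because protocol 5.1 requires background csDMARDs and protocol 5.4 allows low-dose oral corticosteroids. Two things are at stake. A real drug effect may be diluted by subjects who did not change, and chance differences in entry status between small groups may look like safety differences. This matters most at the interim, where the PCS count is the named categorical summary for haematology.

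**Working it through.** **Is the missing condition supplied elsewhere?**

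- SAP 9.1 limits summaries to subjects with both baseline and post-baseline values, but for mean and change statistics. It sets no PCS window.
- SAP Appendix C gives criteria and no window.
- Protocol 7.4 describes the same tables without a post-baseline or worsening condition.
- SAP 9.2.1 does define an on-treatment window (first dose to 30 days after last dose), but for adverse events only.
- The liver table is explicitly post-baseline, so the SAP states the restriction in one place and omits it in the other.

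**Which criteria are exposed?** Lymphocytes, neutrophils, WBC, platelets, transaminases and CPK are graded on absolute levels or multiples of the normal limits. Haemoglobin is graded mainly on the decrease from pre-treatment, with an absolute limb only at Grades 3 and 4. Creatinine has a multiple-of-baseline limb and a ULN limb.

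**Size.** The plan gives no PCS rate, so there is no figure to reproduce. All three quantities below are assumptions:

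- b = share meeting the criterion at baseline
- i = new onset among those normal at baseline
- s = share of the baseline-abnormal whose grade worsens, set equal to i

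Rule as written: b + (1 − b) × i. Worse-than-baseline rule: b × s + (1 − b) × i, which equals i when s = i.

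For b = 30% and i = 5%: as written, 0.30 + 0.70 × 0.05 = 33.5%; restricted, 0.30 × 0.05 + 0.70 × 0.05 = 5.0%.

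| b | As written, i = 5% | Restricted | As written, i = 10% | Restricted |
|---|---|---|---|---|
| 0% | 5.0% | 5.0% | 10.0% | 10.0% |
| 5% | 9.75% | 5.0% | 14.5% | 10.0% |
| 10% | 14.5% | 5.0% | 19.0% | 10.0% |
| 20% | 24.0% | 5.0% | 28.0% | 10.0% |
| 30% | 33.5% | 5.0% | 37.0% | 10.0% |

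For b between 5% and 30% the ratio runs from 14.5/10 = 1.45 to 33.5/5 = 6.7. For scale, the completion estimate in SAP 2.4 implies 40/0.20 = 120/0.60 = 200 subjects. The last row at i = 5% is then 67 against 10 subjects.

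**Would adding post-baseline alone be enough?** No. An abnormality that persists is measured again at each visit, so a subject who stays at the entry grade still qualifies. If all entry abnormalities persist, a post-baseline-only rule gives the same 33.5%.

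**Dilution.** Take b = 30% in two groups with i = 5% and 15%. As written, the groups show 33.5% and 0.30 + 0.70 × 0.15 = 40.5%. A threefold ratio becomes 40.5/33.5 = 1.2, and a 10-point gap becomes 7.

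**Chance imbalance.** With 200 subjects split equally over the six from-to groups (about 33 each, an assumption), the standard error of a between-group difference from entry status alone at b = 30% is √(2 × 0.3 × 0.7 / 33) = 0.113, or about 11 points.

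**The case against.** The strongest reply is that the same section already plans the analysis wanted. Baseline and post-baseline values are graded on the same criteria and cross-tabulated, and the cells above baseline grade in the baseline-by-maximum table are essentially the restricted count. That stands for the final report. It does not cover the interim, because SAP 11 names PCS counts and not shift tables. Mean change, which SAP 11 does name, cannot show how many subjects newly cross a threshold.

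The magnitudes rest on assumption, and that also stands. No entry prevalence or group size is given. Prevalence depends on which grade counts as PCS, and a high figure is most plausible if Grade 1 counts. Protocol 5.1 excludes subjects whose laboratory values meet the feeder study's toxicity criteria; those thresholds are not shown but may limit severe entry abnormalities. No formal between-group PCS comparison is planned, so the 11 points bear only on comparison by eye.

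A worsening condition also has a price: a subject with a persistent severe grade from entry leaves the PCS percentage. The shift tables keep that subject visible.

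A reader might go further and infer that the SAP reports pre-existing abnormalities as effects of study drug. The documents do not support this. The SAP is silent on the window and never calls the PCS counts treatment-emergent. Nor can one infer that every criterion is affected, given haemoglobin and creatinine, or that the listings omit baseline grade, since their columns are unspecified.

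**Conclusion.** The point holds as a gap in the counting rule with a real consequence for some criteria. Followed as written, the rule lets unchanged entry abnormalities into the PCS counts for absolute-level and ULN-multiple criteria, and a sensible post-baseline reading would still let them in. The effect is nil if nobody is abnormal at entry. Under assumed entry prevalences of 5% to 30% and new onset of 5% to 10%, the count is 1.45 to 6.7 times the worse-than-baseline count. These are illustrations, not trial figures. The consequence is limited in the final report by the shift tables and is greater at the interim, where they are not named. The change should be made; it does not put the study's design or its efficacy analyses in question.

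**What to change.** Reword the PCS sentence in SAP 9.3 as follows:

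- Count subjects with at least one post-baseline value, within a stated on-treatment window, whose grade is worse than the baseline grade. The adverse-event window in SAP 9.2.1 is an available model.
- Use as denominator the subjects with a baseline value and at least one post-baseline value.
- Show the baseline grade in the listings.
- For the placebo-to-ABBV-599 group, start the window at the first ABBV-599 dose and take the last value before it as the comparison value. Otherwise an abnormality that arose on placebo in the feeder study is both post-baseline and worse than baseline, and is still counted.
- State which grade counts as PCS, because the rule cannot be programmed unambiguously without it.
- Keep the shift tables and add them to the interim outputs in SAP 11.

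The vital-sign PCS sentence in SAP 9.4 lacks the same window. Most of its criteria add a change-from-baseline limb, but the absolute limbs need the same check.

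The cost is a short SAP edit, a filter in the programs and one more set of interim tables. No new data are needed. What is given up is the count of subjects who keep their entry grade, which the shift tables retain.

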#### **9.4 Analysis of Vital Signs**

Vital sign variables include sitting systolic blood pressure, sitting diastolic blood pressure, pulse, body temperature, and weight. The criteria for potentially clinically significant vital sign findings are presented in [Appendix C](#).

Mean changes from Baseline to post-baseline visits will be summarized with the baseline mean, the visit mean, change from baseline mean, standard deviation, and median. An ANOVA model with only treatment as a factor, not controlling for baseline, will be used to test statistical significance for the mean change from baseline.

The number and percentage of subjects meeting the criteria for potentially clinically significant vital sign values will be summarized.

Vital sign variables will be evaluated based on potentially clinically significant (PCS) criteria ([Appendix C](#)). For each vital sign PCS criterion, the number and percentage of subjects who have a vital sign value meeting the criteria will be summarized. Listings will be provided to summarize subject-level vital sign data for subjects meeting PCS criteria.

#### **9.5 Safety Subgroup Analyses**

No planned safety subgroup analyses.

#### **9.6 Other Safety Analyses**

ECG is collected at Weeks 18, 24, 30, 36, 48, and 60. ECG findings will be summarized by treatment group for each parameter and visit.

## **10.0 Other Analyses**

No other analyses are planned.

## **11.0 Interim Analysis**

An interim analysis to review long-term safety and efficacy will be conducted after Study M16-063 Week 12 database lock and analysis. The descriptive statistics will be presented for key efficacy and safety endpoints with all available data at the interim analysis. Key efficacy endpoints include DAS28(CRP), CDAI, ACR20/50/70, Patient's Assessment of Pain [using visual analog scale, VAS], and HAQ-DI. Key safety endpoints include overview of TEAE, TEAEs reasonably possibly related to study drug, SAEs, TEAE leading to death, AESIs, mean change from baseline for hematology and chemistry, PCS for hematology and chemistry and liver-related elevations.

Unblinded interim analyses for safety will be conducted by a DMC to review safety. The sponsor, study sites and subjects will remain blinded for the duration of the study until the database lock of Study M16-063.

An internal data monitoring committee (DMC) will review unblinded safety data from the ongoing study. The primary responsibility of the DMC will be to protect the safety of the subjects participating in this study. A separate DMC charter has been prepared outside of the protocol and describes the roles and responsibilities of the DMC members, frequency of data reviews, relevant safety data to be assessed, and expectations for blinded communications.

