4 INVESTIGATIONAL PLAN

4.1 Overall Study Design and Plan

This is a Phase 2, double-blind, multicenter, long-term extension (LTE) study to assess the safety, tolerability, and efficacy of ABBV-105 and ABBV-599 in RA subjects who have completed Study M16-063. Subjects who meet eligibility criteria (Section 5.1) and enter the study on ABBV-105, ABBV-599, or upadacitinib from Study M16-063 will continue on their previously-assigned treatment through the end of the LTE study. Subjects who meet eligibility criteria and enter the study on placebo for both ABBV-105 and upadacitinib from Study M16-063 will receive ABBV-599. Study drug treatment assignments include the following:

[figure not shown]
- Group 1: ABBV-599 (ABBV-105 60 mg and upadacitinib 15 mg) administered once a day (QD),
- Group 2: ABBV-105 60 mg and upadacitinib placebo QD,
- Group 3: ABBV-105 20 mg and upadacitinib placebo QD
- Group 4: ABBV-105 5 mg and upadacitinib placebo QD, and
- Group 5: Upadacitinib 15 mg and ABBV-105 placebo QD.

This study plans to enroll subjects who completed Study M16-063 at approximately 39 sites in Canada and the European Union. The number, allocation, and location of sites may vary depending on operational aspects of the study. Study sites and subjects will remain blinded for the duration of the study.

The duration of the LTE study will be approximately 52 weeks. This includes a 48-week double-blind treatment period with study visits conducted at Weeks 18, 24, 30, 36, 48, and 60 from the baseline visit of Study M16-063. In addition, subjects will also have a telephone follow-up call 30 days after their last visit to determine the status of any ongoing AEs/SAEs or the occurrence of any new AEs/SAEs.

The schematic of the study is shown in Figure 1. Further details regarding study procedures are located in the Operations Manual.

Figure 1. Period 1 Schematic

QD = administered once a day

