4.2 Discussion of Study Design

Choice of Control Group

Subjects will roll over from Study M16-063 and continue on their originally randomized treatment, with the exception of those originally randomized to placebo, who will roll over to ABBV-599. The objective of this LTE study is to evaluate long term safety and efficacy of ABBV-105 and ABBV-599, and thus primary comparison will be relative to the safety and efficacy profile observed in each arm during the initial randomized study.

Appropriateness of Measurements

Standard statistical, clinical, and laboratory procedures will be utilized in this study. All efficacy measurements in this study are standard for assessing disease activity in subjects with RA. All clinical and laboratory procedures in this study are standard and generally accepted.

Suitability of Subject Population

This LTE study will enroll subjects who have completed Study M16-063. Only those subjects who have met all of the specified eligibility criteria will have an option to enter into the LTE study to receive

continued therapy, provided the subject is willing and the investigator believes that continuing therapy is appropriate.

Selection of Doses in the Study

Since the study is a continuation of the initial Phase 2 dose exploration study of ABBV-105 and ABBV-599, the doses selected for this study are the same as those used previously in Study M16-063. These doses were determined based on an analysis of pharmacokinetic, pharmacodynamic, and safety data from Phase 1 studies in healthy volunteers for ABBV-105 and Phase 2 and Phase 3 studies for upadacitinib, in addition to efficacy data for upadacitinib in RA.

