5.8 Randomization/Drug Assignment

All subjects were assigned a unique identification number by the IRT at the screening visit for Study M16-063. Subjects who enter the study on active ABBV-105 and/or upadacitinib from Study M16-063 will continue on their previously-assigned treatment through the end of the LTE study. Subjects who previously received placebo treatment during Study M16-063 will receive ABBV-599 in the LTE study.

All AbbVie personnel with direct oversight of the conduct and management of the trial (with the exception of AbbVie Drug Supply Management Team), the investigator, study site personnel, and the subject will remain blinded to each subject's treatment throughout the study. To maintain the blind, the ABBV-105 capsules and matching placebo capsules and upadacitinib tablets and matching placebo tablets provided for the study will be identical in appearance.

In the event of a medical situation that requires unblinding of the study drug assignment, the Investigator is requested to contact the AbbVie Therapeutic Area Medical Director prior to breaking the blind. However, if an urgent therapeutic intervention is necessary which warrants breaking the blind prior to contacting the AbbVie Therapeutic Area Medical Director, the Investigator can directly access the IRT system via the Unblind Subject transaction, which is available to the Investigator. If the IRT system is unavailable, unblinding may occur by contacting EndPoint technical support via either phone (preferred) or email ([contact]). For country-specific phone numbers, please see the following website: <http://www.endpointclinical.com/help-desk/>. In the event that the blind is broken before notification to the AbbVie Therapeutic Area Medical Director, we request that the AbbVie Therapeutic Area Medical Director be notified within 24 hours of the blind being broken.

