APPENDIX D. ACTIVITY SCHEDULE

The following table shows the required activities across the 8 subject encounters. The individual activities are described in detail in the **Operations Manual**.

	LTE Baseline/ Week 12*	Week 18	Week 24	Week 30	Week 36	Week 48	Week 60/PD	Follow-up call (30 days after last dose)
		± 7 days	± 7 days	± 7 days	± 7 days	± 7 days	± 7 days	
Subject information and informed consent	✓							
Eligibility criteria	✓							
Medical and surgical history	✓							
Prior/concomitant therapy	✓*	✓	✓	✓	✓	✓	✓	✓
AE assessment		✓	✓	✓	✓	✓	✓	✓
Patient Questionnaires: 
 • Patient's Assessment of Pain (VAS) • PtGA • HAQ-DI • Morning Stiffness 	✓*	✓	✓	✓	✓	✓	✓	
TJC68/SJC66	✓*	✓	✓	✓	✓	✓	✓	
PhGA	✓*	✓	✓	✓	✓	✓	✓	
12-lead ECG	✓*	✓	✓	✓	✓	✓	✓	
Body weight	✓*	✓	✓	✓	✓	✓	✓	
Vital signs	✓*	✓	✓	✓	✓	✓	✓	
Physical exam	✓*	✓	✓	✓	✓	✓	✓	
Local urine pregnancy test (for all female subjects of childbearing potential)	✓*	✓	✓	✓	✓	✓	✓	
Dispense urine pregnancy tests for monthly home testing	✓	✓	✓	✓	✓	✓		
Local laboratory test - Erythrocyte sedimentation rate (ESR)	✓*	✓	✓	✓	✓	✓	✓	

	LTE Baseline/ Week 12*	Week 18	Week 24	Week 30	Week 36	Week 48	Week 60/PD	Follow-up call (30 days after last dose)
		± 7 days	± 7 days	± 7 days	± 7 days	± 7 days	± 7 days	
Central laboratory tests: 
 Hematology Blood chemistry Urinalysis hsCRP 	✓*	✓	✓	✓	✓	✓	✓	
Central laboratory test - TB screen (QuantiFERON-TB Gold test or interferon gamma release assay [IGRA] equivalent and/or local purified protein derivative [PPD] skin test) or T SPOT®.TB test**						✓		
Optional biomarker sample: Whole blood (serum, plasma, RNA, and DNA)	✓*		✓			✓		
Drug assignment	✓							
Dispense study drug and subject dosing diary	✓*		✓		✓	✓		
Review study drug returned and perform drug reconciliation	✓*	✓	✓	✓	✓	✓	✓	
Reminder to subjects to perform their weekly at-home temperature monitoring***	✓*	✓	✓	✓	✓	✓	✓	

* Tests/study activities are only to be performed if not done as part of Study M16-063.

** As available and if compliant with local TB guidelines (Canada only).

*** As described in Section 6.2.

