## **1.0 Introduction**

This Statistical Analysis Plan (SAP) describes the statistical analyses for ABBV-599 Study M16-763.

Study M16-763 evaluates the long-term safety, tolerability, and efficacy of ABBV-105 and ABBV-599 in RA subjects who have completed Study M16-063.

The SAP will not be updated in case of administrative changes or amendments to the protocol unless the changes impact the analysis.

Unless noted otherwise, all analyses will be performed using SAS Version 9.4 (SAS Institute Inc., Cary, NC 27513) under the UNIX operating system.

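### SAP 11.0 ends the blind for sites and subjects at the feeder study's database lock, against protocol 4.1, protocol 5.8 and SAP 2.3

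*SAP*

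**What the plan says.** SAP 1.0 fixes the scope of the plan: "This Statistical Analysis Plan (SAP) describes the statistical analyses for ABBV-599 Study M16-763". In SAP 11.0, which covers the interim analysis, the rule on blinding is: "The sponsor, study sites and subjects will remain blinded for the duration of the study until the database lock of Study M16-063". One list of three parties (sponsor, sites, subjects) governs the whole sentence.

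Three other sections state the blind with no earlier end:

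- Protocol 4.1: "Study sites and subjects will remain blinded for the duration of the study".
- SAP 2.3, the section on treatment assignment and blinding, repeats that sentence.
- Protocol 5.8: "the investigator, study site personnel, and the subject will remain blinded" to each subject's "treatment throughout the study. To maintain the blind". The same sentence also covers part of the sponsor: "All AbbVie personnel with direct oversight of the conduct and management of the trial (with the exception of AbbVie Drug Supply Management Team").

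Protocol 7.5 plans an unblinded interim analysis of the extension after the feeder's Week 12 lock and analysis. SAP 11.0 puts the interim at the same point. Both sections base it on the data that have accrued by then.

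**The concern.** The SAP 11.0 sentence names two end points that do not coincide. In a plan written for M16-763, the duration of the study runs to the end of the extension. The lock of M16-063 belongs to the feeder and comes before an interim look at the extension. Taken at its word, the closing clause lets the blind of sites and subjects lapse part-way through the extension.

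This would matter because the feeder arm fixes the extension arm. Protocol 4.2 says: "Subjects will roll over from Study M16-063 and continue on their originally randomized treatment, with the exception of those originally randomized to placebo". The placebo subjects all move to ABBV-599. Anyone who knows a subject's feeder assignment therefore knows the current treatment. Many of the outcomes are open to influence by that knowledge:

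- Of the seven ACR components in protocol 3.2, all but hsCRP are scored by the subject or an assessor.
- All four CDAI components in protocol 5.4 are scored in the same way.
- Causality of adverse events is an investigator's judgement (protocol 6.1).

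**Working it through.** **1. Reproduce the plan's durations.** Inputs: the extension's baseline is the feeder's Week 12 (column header in protocol Appendix D), the last treatment visit is at Week 60, and the follow-up call is 30 days later (protocol 4.1).

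- Treatment period: 60 − 12 = 48 weeks, as stated.
- Total: 48 + 30/7 = 48 + 4.3 = 52.3 weeks, which agrees with the stated figure of about 52.

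**2. Place the feeder's lock.** Protocol 7.5 and SAP 11.0 put the extension's interim after the feeder's Week 12 lock. An interim on the data then available implies that the extension is still running. So the lock is an event during the extension, not its end.

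**3. Set the sections side by side.**

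| Section | Sites and subjects blinded until | Sponsor |
|---|---|---|
| Protocol 4.1 | End of M16-763 | Not addressed |
| SAP 2.3 | End of M16-763 | Not addressed |
| Protocol 5.8 | End of M16-763 | Direct-oversight staff, except drug supply, blinded throughout |
| SAP 11.0 | Feeder's lock, on the literal clause | Feeder's lock |

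For sites and subjects, SAP 11.0 is the odd one out against three.

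**4. Ask when the two end points would agree.** For the last subject to roll over, treatment is complete at the feeder's lock only if the lock comes at least 48 weeks after that subject's Week 12 visit. Adverse events are collected to 30 days after the last dose, so causality judgements are out of reach only after about 52.3 weeks.

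**5. Illustrate with assumed lags.** The documents give no lock date. The lags below are assumptions that show how the arithmetic behaves. Extension visits fall at Weeks 18, 24, 30, 36, 48 and 60 minus 12, that is at extension weeks 6, 12, 18, 24, 36 and 48. One month = 365.25/12/7 = 4.35 weeks. Visit windows and dropout are ignored.

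| Assumed lag from last roll-over to lock | Lag in weeks | Treatment weeks left | Visits left of 6 |
|---|---|---|---|
| 1 month | 4.35 | 48 − 4.35 = 43.7 | 6 |
| 2 months | 8.70 | 48 − 8.70 = 39.3 | 5 |
| 4 months | 17.39 | 48 − 17.39 = 30.6 | 4 |

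These figures are for the last subject to roll over. Subjects who entered earlier would have less time left, and those who entered more than about 52 weeks before the lock would have none.

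**The case against.** The strongest reply is that this is a matter of wording with little behind it. Sites work from the protocol and the Operations Manual, and protocol 4.1 and 5.8 are plain. No analysis depends on the clause, and the harm needs an unblinding step that appears nowhere. All of this stands, and it is why the risk is rated low.

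A second reply is that the study in the SAP 11.0 sentence may be the feeder. The text may have been carried over, much as protocol 3.3 describes the monitoring committee's task in terms of M16-063. The sentence would then have a single end point. That may be how it arose, but it does not rescue it. The next paragraph of SAP 11.0 uses the same term for the trial that this SAP covers. Applied to extension sites and subjects, the sentence still ends the blind earlier than SAP 2.3 does. A wrong study number, with M16-763 intended, is just as plausible and also needs correcting.

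A third reply concerns the sponsor. For the sponsor, the clause fits protocol 7.5, which expects unblinded results after the feeder's lock. That is fair. The tension on the sponsor side lies mainly between protocol 5.8 and protocol 7.5. It may be only apparent, because 5.8 covers staff with direct oversight and other staff could run the interim.

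A reader might infer that the plan means to unblind sites at the feeder's lock. The documents do not support this. The clause sets an end to the blind but orders no disclosure, and the only site-level unblinding described is for a medical situation in a subject (protocol 5.8).

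**Conclusion.** The inconsistency is real and limited. On its literal wording, SAP 11.0 lets the blind of sites and subjects end during the extension, against three sections that say otherwise. It is probably a drafting slip or a wrong study number.

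If it were followed, subjective efficacy scores to Week 60 and causality judgements to the 30-day call, about 52 weeks after roll-over, could be made with the arm known. The conclusion that the lock falls during the extension rests on the planned order of lock and interim, not on a date. For that reason no number of weeks or visits can be claimed as lost; the lag figures above are illustrations only.

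A reader might also infer that an error rate for efficacy is compromised. It is not: efficacy is descriptive (protocol 7.3), and SAP 12.0 plans no efficacy hypothesis tests.

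The sponsor's access to unblinded data is a separate, minor point of clarity and not a further fault in this clause.

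**What to change.** In SAP 11.0, for sites and subjects, either delete the closing clause or replace the feeder's lock with the M16-763 database lock. Investigators, site personnel and subjects then stay blinded to subject-level assignment for the whole of M16-763. Naming the M16-763 lock has one advantage: protocol section 11 ends the study at the last follow-up call, so deletion alone leaves the time between last contact and lock unstated.

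Separately, give the sponsor a sentence of its own. It should say which sponsor roles may see unblinded data after the M16-063 lock, so that the unblinded interim in protocol 7.5 is reconciled with protocol 5.8, under which staff with direct oversight, except drug supply, stay blinded throughout.

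The cost is one reworded sentence and one added sentence. No data collection, analysis or trial procedure changes.
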